5.1. Subject inclusion criteria

- 5.1.1. Male and non pregnant female human subjects
- 5.1.2. 21 to 80 years old
- 5.1.3. Subjects who need to undergo arthrocentesis following medical assessment by the Clinician:
Patients diagnosis of Osteoarthritis is based on standard protocol which includes detailed medical history, blood test if necessary, to exclude other causes like RA, gout etc. and confirmed on standing view X Ray findings.

Patients will also be graded (stages of OA) based on that X Rays as well. Only those with primary OA will be included. Diagnosis would be determined during prior appointment(s) with the clinician.

Evidence of effusion is determined by manual palpation of the knees directly. There is no need to use ultrasound scan to determine the presence of effusion. Basically, if it can be “felt”, it can be tapped.

- 5.1.4. Willingness to follow the protocol requirements

5.2. Subject exclusion criteria

- 5.2.1. Known allergy to shellfish
- 5.2.2. Known history of hypersensitivity to Glucosamine or related drugs.
- 5.2.3. Known history of hypersensitivity to Capsaicin (Capsicum extract)
- 5.2.4. Known history of skin sensitivity
- 5.2.5. Subjects who have taken any kind of glucosamine during the last 24 hours
- 5.2.6. Subjects who have taken any kind of treatment for joint pain during the last 24 hours
- 5.2.7. Subjects having scars/cut/dermatological abnormality at application site
- 5.2.8. Pregnant or nursing women

5.3. Subject withdrawal criteria

Subjects are free to withdraw at any time, without giving a reason. This will not affect the standard of care they receive.

6. Treatment of Subjects

6.1. The treatment to be administered

- 6.1.1. Name: Topical Glucosamine cream, Lynk Biotechnologies Pte Ltd, TGC® Transdermal Glucosamine Cream Plus Capsaicin containing 10% w/w Glucosamine Sulphate.2 KCl, presented as a finished product.
- 6.1.2. Manufactured by DynaLynk Pharma Pte Ltd. GMP certified.
- 6.1.3. Dose: A single dose of 2g (containing 200mg of Glucosamine Sulphate. 2KCl) of the Test product will be applied topically on the knee of the subjects (for Test Group only).
- 6.1.4. Dosing schedule: single dose for subjects of the Test group only. Subjects from the Control Group will not receive any treatment.
- 6.1.5. Route / mode(s) of administration: topical application on the affected knee
- 6.1.6. Follow-up – Not applicable

6.2. Medication(s) / treatment(s) permitted (including rescue medication) and not permitted before and/or during the trial.

Please refer to the exclusion criteria in section 5.2. There is no rescue medication needed.

6.3. Procedures for monitoring subject compliance.

There is no need to monitor the patient’s compliance since the Test product (single dose) will be applied by the nurse on the trial site and the extraction of the synovial fluid will be done by the PI.

7. **Assessment of Efficacy**

There is no efficacy being promoted with a single dose application of the Test product. The objective of the study is to assess the bioavailability of the Test product: in the synovial fluid of OA joints.

8. **Assessment of Safety**

Based on the history of usage of the Test product over the last 10 years with over 250,000 tubes sold, the only adverse effect reported by the consumers relates to minor rashes. Less than 10 complaints of this nature have been received over this period. Adverse side effects related to the Test product topical application are extremely rare.

The emergency number to call when required is [name] (T&T FAMILY HEALTH CLINIC & SURGERY) or [name] (Lynk Biotechnologies' main line). Subjects may also contact Temasek Polytechnic IRB for any questions. IRB contact number is: [name]. These contact numbers are given to each subject in the Informed Consent Form.

Adverse events will be recorded in adverse event form or appropriate documents. We will report to Temasek Polytechnic IRB, within 7 calendar days, the occurrence of any serious adverse events, adverse drug reactions and unanticipated episodes that may occur in the course of this research.

All serious adverse events (SAEs) that are unexpected and related to the Test product will be reported to HSA. The investigator is responsible for informing HSA no later than 15 calendar days after first knowledge that the case qualifies for expedited reporting. For fatal or life-threatening cases, HSA will be notified as soon as possible but no later than 7 calendar days after first knowledge that a case qualifies, followed by a complete report within 8 additional calendar days.

All reports will be sent to the Clinical Trial Branches (HSA), and other official parties requiring them (e.g: IRB).

The PI will take all appropriate measures to ensure the safety of the patients, including referral to a specialist if indicated.

9. **Statistics**

9.1. A description of the statistical methods to be employed, including timing of any planned interim analysis(es), and the level of significance to be used.

Statistical analysis will be performed using a one-sided Z-test, which will be used to determine if the glucosamine content in synovial fluid obtained from the Test group is significantly higher than the glucosamine content in synovial fluid obtained from the Control group. The statistical evaluation will be determined at $P < 0.01$.

9.2. The number of subjects planned to be enrolled. In multicentre trials, the numbers of enrolled subjects projected for each trial site should be specified. Reason for choice of sample size, including reflections on (or calculations of) the power of the trial and clinical justification.

A total of 240 osteoarthritic adult male and female patients (120 for the Test group, and 120 for the Control group) will be enrolled in this study. It is assumed that under single dose and with this study design the planned number of subjects is sufficient to achieve the objective of the study.

The sample sizes are sufficient to assume normality while generating a meaningful statistical comparison using the Z-test.

This trial relies on the scientific analysis of the synovial fluid collected, from patients. Therefore it eliminates patient's subjectivity and bias. Hence the trial sample size could be correspondingly reduced.

All eligible subjects will be included in the analyses.

9.3. Criteria for the termination of the trial.

Subjects participation may be terminated if:

- Allergy occurs after cream application and before tapping of synovial fluid
- Non-compliance to any of the exclusion/inclusion criteria

Subjects are free to withdraw at any time, without giving a reason. This will not affect the standard of care they receive.

9.4. Procedure for accounting for missing, unused, and spurious data.

Using glucosamine concentrations ascertained from the standard addition method, the mean absolute deviation method will be used to eliminate outliers. In addition, non-linear results, with $r^2 < 0.95$, will also be discarded. Data from outliers will be excluded from main analysis.

Missing, unused or spurious data: not applicable in this protocol.

9.5. Procedures for reporting any deviation(s) from the original statistical plan (any deviation(s) from the original statistical plan should be described and justified in protocol and/or in the final report, as appropriate).

Any deviation, if any, will be described in the final report.

9.6. The selection of subjects to be included in the analyses (e.g. all randomised subjects, all dosed subjects, all eligible subjects, evaluable subjects).

All subjects that go for treatment and sign consent form will be part of the study. All samples collected will be analysed.

10. Direct Access to Source Data / Documents

For the purpose of ensuring compliance with the Clinical Trial Protocol, Good Clinical Practice and applicable regulatory requirements, the Investigator should permit auditing by or on the behalf of the Sponsor and inspection by applicable regulatory authorities.

The Investigator agrees to allow the auditors/inspectors to have direct access to his/her study records for review, being understood that these personnel are bound by professional secrecy, and as such will not disclose any personal identity or personal medical information.

The Investigator will make every effort to help with the performance of the audits and inspections, giving access to all necessary facilities, data, and documents.

As soon as the Investigator is notified of a future inspection by the authorities, he will inform the Sponsor and authorize the Sponsor to participate in this inspection.

The confidentiality of the data verified and the protection of the patients should be respected during these inspections.

Any result and information arising from the inspections by the regulatory authorities will be immediately communicated by the Investigator to the Sponsor.

The Investigator shall take appropriate measures required by the Sponsor to take corrective actions for all problems found during the audit or inspections.

11. Quality Control and Quality Assurance

The Quality Assurance department will confirm that the study is conducted in adherence to the protocol for each activity.

In process quality checks and review procedures carried out by the quality assurance department will ensure that the activities and the documentation of the data are done as per the protocol. Deviation from the protocol observed during the quality checks/review will be verified.

12. Ethics

The protocol was reviewed and approved by Temasek Polytechnic IRB. The approval letter is attached in Annex 9.

All the subjects participating in this study will receive full details about the study, the procedures, the risks and the treatment involved by verbal and written form in the Informed Consent Form (Annex 3). Subjects need to sign the Informed Consent Form to confirm their informed agreement to undergo the study.

Remuneration of subjects:

The subjects are already presenting themselves at T&T Family Health Clinic & Surgery for OA treatment.

The subjects who completed the study and agreed to apply the Test product will be adequately compensated. Arthrocentesis cost will be offered free (value \$100 per patient – not per sample).

Patients who do not wish to apply the Test product, but who signed the consent form (i.e Control group) so that their samples can be used for scientific research will be offered a free 45g tube of the Test product.

There is no added inconvenience or impost on them besides the application of a cream on the affected knee. Therefore, the reimbursement is fair and reasonable.

13. Data Handling and Record Keeping

13.1. The holder of the certificate will keep adequate clinical records of each subject for the duration of the clinical trial.

13.2. The holder of the certificate will ensure that such records are:

13.2.1. Kept up to date at all times;

13.2.2. Available at all times for inspection by the licensing authority or any person authorised by him in that behalf; and

13.2.3. Kept at least for whichever of the following periods expires later:

- until there are no pending or contemplated marketing applications of the Test product in Singapore;
 - 2 years after the last approval of a marketing application for the test material in Singapore;
 - where the clinical trial is discontinued, 2 years after the licensing authority has been informed of the discontinuation of the clinical trial under regulation 9;
 - 6 years after the completion of the clinical trial; or
 - such other period as the licensing authority may direct.
- 13.3. The holder of the certificate will maintain a record containing the names and such other particulars of every person assisting or participating in a clinical trial.

14. Financing and Insurance

14.1. Source of funding for the study: the Sponsor.

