4.2. Trial design

This is an open label, single dose design to examine the glucosamine content in the synovial fluid after applying the Test product on OA patient's knee.

4.3. Procedure flowchart:

4.4. A description of the measures taken to minimise / avoid bias, including randomisation / blinding:

The analytical results are objective. There is no possibility of subjective bias or placebo effect. Therefore there is no measure necessary and hence no randomization needed.

As for the selection of subjects, there is no need to have measures to minimise bias. There is no bias since we take all patients that come in to the clinic for treatment. Patients are not selected for control or test group, they select themselves by choosing (yes or no) to apply the Test product.

- 4.5. A description of the trial treatment(s) and the dosage and dosage regimen of the investigational product(s). This also includes description of the dosage form, packaging, and labelling of the investigational product(s).

A single dose of 2g of the Test product will be applied topically on the affected knee of the Test Group subjects. The Test product is presented in a white tub, labelled with the product name, Batch Number and Expiry date.

- 4.6. The expected duration of subject participation, and a description of the sequence and duration of all trial periods, including follow-up, if any.

Single session, up to 4 hours, for the cream application and joint's fluid aspiration. The tapping of synovial fluid should be done between 1 and 3 hours following cream application (for the Test group). No follow-up needed.

- 4.7. A description of the "stopping rules" or "discontinuation criteria" for individual subjects, parts of trial and entire trial.

Subjects participation may be terminated if:

- Allergy occurs after cream application and before tapping of synovial fluid
- Non-compliance to any of the exclusion/inclusion criteria

Subjects are free to withdraw at any time, without giving a reason. This will not affect the standard of care they receive.

- 4.8. Accountability procedures for the investigational product(s), including the placebo(s) and comparator(s), if any.

There is no risk of any mix up since there is no comparator or placebo arm in this study.

- 4.9. Maintenance of trial treatment randomisation codes and procedures for breaking codes.

The subjects will be identified via subject ID, a 3 digits number (e.g: 123). Samples will be labelled with the subject ID.

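### The Test group's fee waiver depends on completing the study, which may discourage subjects from reporting symptoms before the tap or withdrawing once the cream is on

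*Combined protocol and SAP*

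**What the plan says.** - **Test-group compensation (section 12, Remuneration of subjects).** "The subjects who completed the study and agreed to apply the Test product will be adequately compensated". The next sentence names the benefit: "Arthrocentesis cost will be offered free", with a stated value of $100 per patient.
- **Control-group compensation (same section).** The wording for patients who decline the cream is: "but who signed the consent form (i.e Control group) so that their samples can be used for scientific research will be offered a free 45g". Their benefit, a tube of the cream, is tied to signing consent; no completion condition is stated.
- **Stopping an individual (sections 4.7 and 9.3).** "Subjects participation may be terminated if", among other grounds, "Allergy occurs after cream application and before tapping of synovial fluid".
- **Withdrawal (sections 4.7, 5.3 and 9.3).** "Subjects are free to withdraw at any time, without giving a reason. This will not affect the standard of care they receive". Payment is not mentioned.
- **Timing (section 4.6).** There is one session of up to 4 hours, with the tap 1 to 3 hours after application. "No follow-up needed".
- **Safety recording (section 8).** Adverse events in general are to be recorded. The readable text describes no scheduled skin check.

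**The concern.** Sections 2.3 and 2.6 make clear that these patients attend for arthrocentesis on their own initiative and that the procedure is independent of the trial. A subject who stops after the cream therefore still needs the tap. Because the benefit is the price of that tap, losing it would be a real cost, and it would fall after the subject has already accepted the trial's only added risk, the topical application (section 2.3).

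Two things are at stake. The first is safety reporting: a subject with itch or burning before the tap has a financial reason to keep quiet. The second is voluntariness: a subject who wants to stop has a financial reason to stay. Both fall on exposed subjects only, because the Control benefit carries no such condition.

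**Working it through.** **Step 1: follow the written rules for a Test subject after application.**

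| Event after application | Relevant text | Waiver under section 12 |
|---|---|---|
| Tapped as planned | Sections 4.6, 12 | Kept |
| Allergy before the tap, participation ended | Sections 4.7, 9.3, 12 | Not stated; on a plain reading not a completer, so may be lost |
| Symptom before the tap, participation not ended | Sections 4.7, 9.3 (permissive) | Kept |
| Withdraws before the tap | Sections 4.7, 5.3, 9.3, 12 | Not stated; on a plain reading may be lost |
| Reaction after the tap, within the session | Sections 4.6, 8 | Not evidently affected |

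The second and fourth rows are the problem. The uncertainty sits between application and tap.

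**Step 2: how many subjects might be affected.** The plan gives no reaction rate. Its only related figure is the complaint history in sections 2.3 and 8: fewer than 10 complaints over more than 250,000 tubes.

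- Rate: below 10 / 250,000 = 0.00004, or 0.004% per tube.
- Expected cases in 120 Test subjects: below 120 × 0.00004 = 0.0048.

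This is a count of spontaneous complaints per tube, not an incidence per person, so it probably understates the rate. A range of assumed true pre-tap reaction rates p is shown instead, with expected cases = 120p and chance of at least one = 1 − (1 − p)^120.

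| Assumed p | Expected cases | Chance of at least one |
|---|---|---|
| 0.1% | 0.12 | 11% |
| 1% | 1.2 | 70% |
| 2% | 2.4 | 91% |
| 5% | 6 | 99.8% |

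**Step 3: why a few unreported reactions could matter.** If none of 120 subjects is recorded with a reaction, the exact one-sided 95% upper limit on the rate is 1 − 0.05^(1/120) = 2.5%. With so few expected events, one or two unreported cases would change the safety description.

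**Step 4: effect on the primary comparison.** The plan gives 120 per group and a one-sided Z-test at 0.01 (sections 9.1 and 9.2), but no effect size, SD or power. For scale only, assume a standardised difference d = 0.41, chosen because it gives about 80% power. Power = Φ(d / √(1/n₁ + 1/n₂) − 2.326).

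- 120 and 120: 0.41 / 0.1291 − 2.326 = 0.85, power 80.2%.
- 114 and 120 (all 6 subjects from the 5% row lost): 0.41 / 0.1308 − 2.326 = 0.81, power 79.1%.

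The loss is about one percentage point at the top of the assumed range.

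**The case against.** The best reply is that the documents ask only for clarification. Termination is discretionary, and its trigger is allergy, so a mild reaction need not end participation. Completion is undefined, and no sentence takes the waiver away from someone stopped for allergy. The consent form (Annex 3) was not available to this review and may already settle the matter. A nurse applies the cream on site and the investigator taps the same knee (section 6.3), so a visible rash could be noticed without the subject saying anything. No endpoint in section 4.1 concerns safety.

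Most of this stands, and it rules out several stronger readings that a reader might infer:

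- *Any subject who reports a skin reaction is terminated and forfeits $100.* The text is permissive and names allergy only, and the forfeiture is an inference from an undefined term.
- *The pre-tap report is the only safety signal in the session.* Section 8 records adverse events generally, and a session of up to 4 hours with a tap at 1 to 3 hours can leave time for observation afterwards.
- *The payment rule contradicts free withdrawal.* That clause protects standard of care and is silent on money.
- *Reactions will be under-reported by a known amount.* Nothing in the documents supports a reaction rate or a proportion staying silent.

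The payment rule itself remains. Section 12 states a completion condition for the Test group, and no readable section makes an exception. A subject cannot know beforehand how the discretion will be used, and itch or burning may not be visible to staff.

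**Conclusion.** The point holds as a matter of ethics and safety reporting. Read plainly, section 12 together with sections 4.7 and 9.3 may cost a Test subject a $100 benefit if they are stopped for allergy or withdraw after application. That is a possible disincentive to speak up before the tap, mainly about symptoms staff cannot see, and it is in tension with voluntary withdrawal.

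The number affected is unknown. The 0.1 to 6 subjects in 120 rest wholly on the assumed rates of 0.1% to 5%, and they count subjects with a reaction, not subjects who would hide one. Withdrawals for other reasons are not included. The primary analysis is hardly touched. The conclusion assumes that completing the study includes having the tap as a study subject, and that the consent form does not already say otherwise.

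**What to change.** In section 12, replace the two conditions on the Test-group benefit (completion and agreement to apply) with a single one: *to whom the Test product was applied*. The waiver then holds whether or not the subject later withdraws, is terminated or gives a usable sample. Check that the consent form says the same, and amend it if it does not.

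The cost is one sentence in the protocol, a check of the consent form, and $100 for each subject who stops after application. If every subject with a reaction in the assumed range stopped, that would be between 0.12 × $100 = $12 and 6 × $100 = $600 in expectation, plus $100 for each withdrawal for other reasons. No dose, clinical rule or analysis changes.

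### Could repeat samples from one patient enter the Z-test as independent values and break its 1% level?

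*Combined protocol and SAP*

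**What the plan says.** The unit of analysis has to be pieced together from several sections of the combined protocol and SAP.

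- **Section 9.1:** "Statistical analysis will be performed using a one-sided Z-test", comparing glucosamine content between Test and Control at P < 0.01. It does not say whether an observation is a patient, a knee or a sample.
- **Section 9.2:** the sample size is counted in patients, "120 for the Test group, and 120 for the Control group", and "All eligible subjects will be included in the analyses". The same section justifies the Z-test by these group sizes.
- **Section 9.6**, on which subjects are analysed: "All samples collected will be analysed".
- **Section 12**, on remuneration: the free arthrocentesis for Test patients is valued "per patient – not per sample".
- **Section 4.6:** participation is a "Single session, up to 4 hours", without follow-up.
- **Sections 4.5 and 6.1.5:** the single dose is "applied topically on the affected knee of the Test Group subjects"; the route is "topical application on the affected knee".
- **Section 4.9:** samples carry the subject ID.

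**The concern.** The payment wording separates patients from samples, and that distinction has an obvious purpose only if one patient can yield several samples. Nothing in the exclusion criteria (5.2) bars a patient with effusions in both knees, or a patient who comes back. Section 9.6 then takes in every sample, under a heading about selection for the analyses, and 9.1 gives no rule for averaging or choosing among them.

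If two samples from one patient entered the Z-test as separate values and were positively correlated, the test would assume more independent information than it has. The standard error would be too small, and the one-sided 1% level of the only primary comparison would be exceeded. An unstated unit also leaves the analyst a choice after the results are known.

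**Working it through.** **The plan's own figure.** 120 + 120 = 240 patients, as stated in 9.2. The plan gives no effect size, standard deviation or power, so 240 cannot be derived further. The one-sided critical value at 0.01 is 2.326.

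**What the text supports.** Two readings must both hold before there is any inflation.

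1. *Patients give repeats.* The only support is the payment phrase in section 12, which sets a reimbursement and not a sampling schedule. No section schedules a second sample, and 4.5, 4.6 and 6.1.5 point the other way. The phrase could also refer to several tubes from one tap: section 2.3 expects 5 to 50 ml per collection.
2. *Repeats enter the test separately.* The support is the sentence in 9.6. Elsewhere the document uses analysis for the laboratory assay (1.4.3, 4.9, and the remark in 9.2 on analysing the fluid). Read that way, 9.6 says only that every sample is assayed.

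**Size if both readings held.** The share p of patients with two samples and the within-patient correlation ρ are assumptions, taken as equal in both groups.

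- Values per group = 120 × (1 + p)
- Design effect DE = 1 + 2pρ/(1 + p)
- True level = P(Z > 2.326/√DE)

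Example, p = 0.1 and ρ = 0.3: DE = 1 + 0.06/1.1 = 1.055; 2.326/√1.055 = 2.265; level 1.17%.

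| p | ρ | Values per group | DE | True level | Simulated, all samples separate | Simulated, one mean per patient |
|---|---|---|---|---|---|---|
| 0 | – | 120 | 1.000 | 1.00% | 1.05% | 1.05% |
| 0.05 | 0.3 | 126 | 1.029 | 1.09% | 1.11% | 1.01% |
| 0.1 | 0.3 | 132 | 1.055 | 1.17% | 1.21% | 1.05% |
| 0.1 | 0.5 | 132 | 1.091 | 1.30% | 1.30% | 1.00% |
| 0.2 | 0.5 | 144 | 1.167 | 1.56% | 1.59% | 1.07% |

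The simulations used normal data, no true difference and 200,000 runs. Their error is about √(0.01 × 0.99/200,000) = 0.02 percentage points.

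**Repeats in one group only** (p = 0.1, ρ = 0.5). True variance over assumed variance = (1.091/132 + 1/120)/(1/132 + 1/120) = 0.01660/0.01591 = 1.043, giving a level of about 1.1%.

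**Precision.** With a sample variance of 1, the variance of the group difference with all samples, against one mean per patient, is:

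- p = 0.1, ρ = 0.3: 2 × 1.055/132 = 0.01598 against 2 × (0.9 + 0.1 × 0.65)/120 = 0.01608; standard-error ratio 1.003.
- p = 0.2, ρ = 0.5: 0.01620 against 0.01583; ratio 0.988.

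An analyst who uses one value per patient therefore gives up almost nothing.

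**The case for a change.** The best argument for a change is that it would be cheap: a sentence or two would fix the unit and remove a choice that could otherwise be made after seeing the data. It is also true that 9.2 says who is included, not how many values each contributes, and that the singular knee in 4.5 and 6.1.5 describes cream application in the Test group and does not limit what is aspirated from Control patients. Section 9.4 likewise does not say whether its outlier and r² exclusions work by sample or by patient.

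The inflation could also be larger than the low cases suggest, since two taps of one knee might correlate above 0.5. At ρ = 0.9, 10% repeats give DE = 1 + 0.18/1.1 = 1.164 and a level of 1.6%. If every patient gave two samples, DE = 1 + ρ, and the level would run from 2.1% (ρ = 0.3) to 4.6% (ρ = 0.9).

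What stands is that the unit is unwritten and that a clarification would do no harm. The larger figures do not stand as a description of this trial, because universal double sampling does not fit a single session with one treated knee. Nor is the remedy as simple as it looks. Averaging treated-knee samples in the Test group but all samples in the Control group would define the outcome differently by group. The labelling described in 4.9 ties a sample to its patient but does not mention the knee.

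**Conclusion.** The concern does not call for a change. The plan leaves out a detail; it does not state a rule that gives a wrong result. Its sample size, its inclusion statement and its description of participation all point to one value per patient. Analysed that way, the 120 against 120 comparison holds its one-sided 1% level. An analyst who meets an occasional second sample can link it through the subject ID and reduce it to one value by the same rule in both groups, with a standard error within about 1% of that from using every sample.

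If repeats were entered separately, the level would be about 1.1% to 1.3% with 5% to 10% repeats and correlation 0.3 to 0.5. A shift of 0.1 to 0.3 percentage points is unlikely to alter a conclusion. These figures rest on an assumed share and correlation, equal in both groups; with no repeats the shift is zero.

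One reservation: the flowchart in 4.3, the Data Record Form and the consent form (Annex 3) were not available for this check. They may state the number of samples per patient. If they showed that repeat taps were routine, the question would need to be reopened.
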